2.1.5.2 Deaths

The deaths observation period are per the observation periods defined above.

- Death on-study: deaths occurring during the on-study observation period.
- Death on-treatment: deaths occurring during the treatment-emergent adverse event period.
- Death post-study: deaths occurring after the end of the study.

2.1.5.3 Laboratory safety variables

Clinical laboratory data consists of blood analysis, including hematology, clinical chemistry, and urinalysis. Clinical laboratory values after conversion will be analyzed into standard international units and international units will be used in all listings and tables.

Blood samples for clinical laboratories will be taken at Visit 1 (Screening), Visit 2 (Day 1), Visit 4 (Week 4), Visit 5 (Week 8), Visit 6 (Week 12), Visit 7/EOT (Week 24), early termination and Visit 8/EOS (Week 35) unless otherwise specified. The laboratory parameters will be classified as follows:

- Hematology
 - **Red blood cells and platelets and coagulation:** Hemoglobin, hematocrit, red blood cell count, erythrocyte sedimentation rate (ESR) and platelet count,
 - **White blood cells:** white blood cell count with differential blood count (neutrophils, lymphocytes, monocytes, basophils, eosinophils),
 - **Tuberculosis screen:** a Quantiferon®-TB gold evaluation.
- Biochemistry
 - **Metabolism:** Fasting glucose, total protein, albumin, high-sensitivity C-reactive protein (hsCRP),
 - **Electrolytes:** sodium, potassium, chloride, calcium, phosphorous, bicarbonate,
 - **Renal function:** serum creatinine, creatinine phosphokinase (CPK), blood urea nitrogen, clearance of creatinine according to Cockcroft and Gault formula (mL per minute) (qualitative variable: <30, [30-50[, [50-80], >80),
 - **Pregnancy test:** (For women of childbearing potential) β-HCG blood test and urine pregnancy tests will be performed,
 - **Liver function:** alkaline phosphate (ALP), Alanine transaminase (ALT), Aspartate transaminase (AST), total bilirubine (TBILI),
 - [REDACTED]
- Serology
 - **Hepatitis screen:** hepatitis B surface antigen, hepatitis B surface antibody, HBV DNA, hepatitis C antibody, hepatitis C RNA, HIV-1/HIV-2 antibody,
 - [REDACTED]
- Urine sample
 - **Urinalysis** (by dipstick): specific gravity, pH, glucose, ketones, occult blood, protein, nitrate, leukocyte esterase, urobilinogen and bilirubin.

Technical formulas are described in [Section 2.5.1](#).

2.1.5.4 Vital signs variables

Vital signs include: systolic and diastolic blood pressure in sitting position (mmHg), weight (kg) and heart rate (beats per minute).

2.1.5.5 Electrocardiogram variables

ECGs were recorded automatically by the device at the Investigator site.

ECG parameters include heart rate (beats per minute), PR interval (msec), QRS duration (msec), QT interval (msec) and corrected QTc (according to Bazett and Fridericia, see [Section 2.5.1](#)), ST deviation (mm), T-wave and U-wave morphologies (category as normal or abnormal).

2.1.6 Pharmacokinetic variables

All measurements (scheduled or unscheduled) will be assigned to analysis windows, as defined in [Section 2.5.4](#), in order to provide an assessment of the PK parameter at each time point planned to be collected as per protocol.

C_{trough} , $C_{trough,av,ss}$) and $C_{Follow-Up}$ will be defined as follows:

- C_{trough} : SAR156597 concentration sample within 2h before each administration (Day 1, Week 4, Week 8, Week 12 and Week 24).
- $C_{trough,av,ss}$: SAR156597 average trough concentrations (“ $C_{trough,av,ss}$ ”) will be calculated for each patient as the mean of “ $C_{troughs}$ ” considered at steady state (ss). The occurrence of steady state will be assessed graphically, by plotting “ C_{trough} ” throughout the study visits over all patients.
- $C_{Follow-up}$: SAR156597 concentration sample taken in Week 35, 12 weeks after last injection.

2.1.7 Immunogenicity variables

All measurements (scheduled or unscheduled) will be assigned to analysis windows defined in [Section 2.5.4](#), in order to provide an assessment of the Anti-SAR156597 antibodies (ADA) parameter at each time point planned to be collected as per protocol.

ADA positive patients are patients with at least 1 treatment-induced or treatment-boosted ADA positive sample during the TEAE period, where:

- Treatment induced ADAs: ADAs developed de novo (seroconversion) following administration of the biotherapeutic (ie, formation of ADAs any time after the initial drug administration in a subject without pre-existing ADAs). If the baseline ADA sample is missing or non-reportable and at least one reportable ADA sample is available during the treatment (including follow-up period) the baseline sample will be considered as “negative” for data analysis. This is considered being a conservative approach for ADA assessment.

- Treatment boosted ADA: Pre-existing ADAs that were boosted to a higher level following administration of biotherapeutic (ie, any time after the initial drug administration) the ADA titer is significantly higher than the baseline titer. A low serial dilution schema (2-fold or 3 fold) should be applied during titration. A difference in titer values of two titer steps between an on treatment or follow-up sample and its baseline sample is considered significant. For examples, at least a 4-fold increase in titers for 2-fold serial dilution schema (or 9-fold increase in titers for 3-fold serial dilution schema). If no titer could be determined for a positive sample, the titer will be reported as the MRD of the assay.

The rest will be classified as ADA negative or inconclusive patients.

The following variables will be described:

- ADA response (Positive, Negative or inconclusive). For ADA positive:
 - Titer levels,
 - Neutralizing status (Positive or inconclusive).
- Pre-existing positive ADA defined as patients with positive ADA response at baseline with less than a specific increase (depending on titer calculation, eg, 4-fold increase in titer for 2-fold serial dilution schema, 9-fold increase in titer for 3-fold serial dilution schema) in the post-baseline period.
- Treatment-emergent positive ADA response defined as 1) Patients with no ADA positive response at baseline but with any positive response in the post-baseline period (up to follow-up visit) or 2) Patients with a positive ADA response at baseline and at least a specific increase (depending on titer calculation, eg, 4-fold increase in titer for 2-fold serial dilution schema, 9-fold increase in titer for 3-fold serial dilution schema) in titer in the post-baseline period (up to follow-up visit). For treatment-emergent positive ADA, the following categories for ADA duration will be applied:
 - A persistent positive response is a treatment-emergent ADA positive response detected in at least 2 or more post-baseline samples separated by at least a 16-week period (irrespective of any negative sample in between),
 - An indeterminate duration positive response is defined as ADA present only at the last sampling time point (and all previous samples negative) or with two last samples are positives but separated by a period less than 16 weeks.
- A transient positive response is defined as
 - Treatment induced ADA detected only at one sampling time during treatment or follow-up observation period (excluding last sampling time),
 - Treatment induced ADA detected at two or more sampling time during treatment where the first and last ADA positive sample are separated by a period less than 16 weeks and last sampling time is negative.
- Duration of ADA defined as longevity of treatment induced ADA (in days): date of last treatment induced ADA sample minus date of first treatment induced or treatment boosted ADA sample + 1. This will be calculated only for subjects with at least 2 positive ADA samples.
- Time to onset of treatment-emergent ADA positive response (in days): date of first ADA positive - date of first IMP administration.

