A placebo-controlled first time in man study (TDU11325 study) has shown that single SC doses ranging from 10 to 300 mg were safe and well tolerated in healthy subjects. After single SC administration of SAR156597 at doses of 10 to 300 mg, peak concentrations of SAR156597 in plasma (C_{max}) occurred, on average, 4 to 7 days after administration. SAR156597 exposure increased with dose but in a less than dose proportional manner. The overall terminal elimination half-life ($t_{1/2z}$) was about 15 days and was independent of dose over the dose range of 10 to 300 mg. Low titers of ADA were detected and confirmed in post-dose plasmas from 4 of 36 subjects who received SAR156597.

[figure not shown]
The repeated ascending dose study (TDR11326) was conducted in patients with Idiopathic Pulmonary Fibrosis (IPF) to evaluate the safety, tolerability, PK and pharmacodynamics of 3 dose levels of SAR156597 (50, 100, and 200 mg) administered SC once a week over a 6-week period (7 administrations) according to a double-blind, randomized, placebo-controlled, sequential

design. A total of 24 patients with IPF were randomized (6 in the placebo group and 18 in the SAR156597 groups). SAR156597 was generally safe and well tolerated. The most commonly reported AEs were infections with a comparable incidence across treatment groups. No significant emergent ADA reactivity developed as a consequence of treatment with SAR156597. Steady state of SAR156597 was achieved on Day 43 for all doses. The results of pharmacodynamic data showed that SAR156597 reduced, in an apparent dose-dependent manner from 50 to 200 mg once a week, the plasma level of TARC (or CCL17), a protein directly induced by IL-4 and IL-13 receptor activation. SAR156597 is currently in Phase 2b of clinical development for the treatment of IPF.

More detailed information is provided in the Investigator's Brochure (IB).

ACT14604 Study

The ACT14604 study will evaluate the efficacy and safety of SAR156597 administered subcutaneously over a 24-week period for the treatment of patients with dcSSc. It will be a multinational, randomized, double-blind, placebo-controlled, 2 parallel group study conducted in patients diagnosed with dcSSc.

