9.3.1.3.2 Anti-drug antibodies

All ADA samples will be analyzed by the Bioanalysis and Biomarkers domain in DSAR OC Montpellier (France).

For the analysis of potential ADAs in human plasma, a validated bridging qualitative ELISA using electrochemiluminescence detection will be used.

Positive samples in screening assay will then be tested in a confirmatory assay (competition with SAR156597) in order to demonstrate the presence of antibodies and eliminate false positive results generated from the initial screening assay.

Interference of SAR156597 in the ADA assay will be documented so that the highest drug concentration that does not affect the limit of ADA detection is known, and the interpretation of immunogenicity takes into account this parameter.

Additional information on the bioanalytical method for ADAs will be provided in the Laboratory Manual.

Samples that are ADA positive will be further evaluated for their potential neutralizing activity with an assay currently in development.

Placebo samples will only be analyzed at baseline, and will continue to be followed if the baseline time point results positive for ADA.

In the interim, the Sponsor will store frozen specific aliquots for neutralizing activity testing if necessary.

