2.1.5 Safety endpoints

The safety analysis will be based on the reported adverse events and other safety information, such as clinical laboratory data, vital signs, ECG.

Observation period

The observation period will be divided into 4 epochs:

- The **pre-treatment** epoch is defined as the time from the signed informed consent date up to the first administration of IMP.
- The **treatment** epoch is defined as the time from the first administration of the IMP to the last administration of the IMP + 7 days.
- The **residual treatment** epoch is defined as the time from the last administration of the IMP + 8 days to the last administration of the IMP + 84 days.

The treatment-emergent adverse event (TEAE) period will include both **treatment** and **residual treatment** epochs.

- The **post-treatment** epoch is defined as the period of time starting the day after the end of the TEAE period up to the end of the study (defined as last protocol-planned visit or last study assessment).

The on-study observation period is defined as the time from the first administration of IMP until the end of the study (defined as last protocol planned visit or last study assessment).

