2.4.7 Analyses of immunogenicity data

The following summaries will be performed on the ADA population, taking into account all samples regardless of timing in relation to injections:

- ADA results (negative, positive or inconclusive) by time point and by treatment arm.
- Neutralizing status (inconclusive or positive) for positive ADA by time point and by treatment arm.

- ADA titers using descriptive statistics (median, Q1, Q3, minimum and maximum) for positive ADA by time point and by treatment arm.
- Number (%) of patients with pre-existing ADA and number (%) of patients with treatment-emergent ADA positive response by treatment arm.
- Number (%) of patients with persistent/transient/indeterminate treatment-emergent ADA positive response by treatment arm.
- Time to onset of treatment-emergent ADA positive response (in days) using descriptive statistics by treatment arm and also according to peak titer.
- Duration of ADA (in days, only for subjects with at least 2 positive ADA samples) using descriptive statistics by treatment arm.

Correlations between ADA parameters (eg, titers, treatment-emergent ADA positive status, neutralizing status) and PK, safety and/or main efficacy endpoint(s) will be explored (eg, scatter plot) according to the study results.

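### SAP 2.1.7 puts two time limits on the same patient-level ADA status, so a patient first positive more than 84 days after the last dose is both treatment-emergent positive and ADA negative or inconclusive

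*SAP*

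**What the plan says.** SAP 2.1.7 first sets a patient-level ADA response: "ADA positive patients are patients with at least 1 treatment-induced or treatment-boosted ADA positive sample during the TEAE period". All remaining patients are classed as negative or inconclusive. The section lists ADA response among the variables to be described, with titer and neutralizing status given for those who are positive.

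The TEAE period comes from SAP 2.1.5. "The treatment-emergent adverse event (TEAE) period will include both" the treatment epoch and the residual treatment epoch, and the latter runs "from the last administration of the IMP + 8 days to the last administration of the IMP + 84 days".

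SAP 2.1.7 then defines a treatment-emergent positive ADA response with two limbs. The first is "Patients with no ADA positive response at baseline but with any positive response in the post-baseline period (up to follow-up visit"). The second is a positive baseline followed by a specified increase "in titer in the post-baseline period (up to follow-up visit"). These are the treatment-induced and treatment-boosted criteria again, over a longer period.

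SAP 2.4.7 produces the ADA summaries "taking into account all samples regardless of timing in relation to injections". Its patient-level incidence line counts treatment-emergent responses.

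ADA blood is drawn at Week 35 (Protocol 10.1.10). Patients who stop treatment early are asked to attend the remaining visits on schedule, including Weeks 24 and 35 (Protocol 1.2, footnote s, and 10.3.4).

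**The concern.** Two definitions of one status, in one section, stop at different times, and nothing in either document reconciles them. A patient whose first positive sample comes more than 84 days after the last dose satisfies the treatment-emergent definition. The same patient fails the ADA-positive definition and so falls into the negative-or-inconclusive group. That patient can even be given an ADA duration category, since the indeterminate category covers a positive found only at the last sampling time, while being labelled not positive in the ADA response variable.

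Immunogenicity is a secondary objective, and Protocol 11.4.4 promises treatment-induced and treatment-boosted incidence together with an assessment of impact on PK, efficacy and safety. The split status would carry into any output restricted to ADA-positive patients. The sample most often caught is Week 35, the one furthest from dosing. That matters because the protocol expects possible drug interference: "Interference of SAR156597 in the ADA assay will be documented".

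**Working it through.** **Inputs**
- Last planned dose: Week 23 (Protocol 1.2, footnote c).
- Week 35 target: study Day 246 (SAP 2.5.4, Table 3); Week 24 target: Day 169 (same table).
- TEAE period ends at last dose + 84 days (SAP 2.1.5).
- Visit window ±2 days (Protocol 1.2, footnote a); dosing window ±2 days (Protocol 8.1.4).
- Assumed treatment discontinuation 10%; 47 patients per arm (SAP 1.3).

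**The plan's own interval.** Study day = 7 × week + 1.
- Last dose: 7 × 23 + 1 = Day 162.
- Week 35: 7 × 35 + 1 = Day 246.
- Gap: 246 − 162 = 84 days = 12 weeks, which agrees with SAP 2.1.6.
- TEAE end: 162 + 84 = Day 246. On the exact schedule the Week 35 sample is the last day inside, with zero slack.

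**Completers within the allowed windows.** Gap = 84 + visit offset − dose offset, each offset from −2 to +2.
- Range: 84 − 4 = 80 to 84 + 4 = 88 days.
- Of the 5 × 5 = 25 combinations, 10 give a gap above 84. If all were equally likely, that is 10/25 = 40%.
- With the last dose exactly on Day 162, visits on Day 247 or 248 are outside: 2 of 5 days.

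**Early stoppers who attend on schedule**

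| Last dose | Dose day | TEAE end (day) | Week 24 (Day 169) | Week 35 (Day 246) |
|---|---|---|---|---|
| Week 22 | 155 | 239 | inside | 7 days outside |
| Week 20 | 141 | 225 | inside | 21 days outside |
| Week 16 | 113 | 197 | inside | 49 days outside |
| Week 12 | 85 | 169 | inside (zero slack) | 77 days outside |
| Week 11 | 78 | 162 | 7 days outside | 84 days outside |

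For a last dose at Week 22, the most favourable use of both windows gives a dose on Day 157 and a visit on Day 244. The gap is then 87 days, still outside. So the Week 35 sample of every early stopper is outside.

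**How many samples.** At 10% discontinuation, 0.10 × 47 = 4.7 patients per arm would have a Week 35 sample outside the TEAE period, if all of them attend. This figure and the 40% count samples outside the window. They do not count misclassified patients: a misclassified patient must also be first positive (or first boosted) at such a sample, and the documents give no rate for that.

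**Drug level at Week 35.** The half-life in the single-dose study "was about 15 days and was independent of dose over the dose range of 10 to 300 mg". 84/15 = 5.6 half-lives, and 0.5^5.6 = 0.021, so about 2% of the drug would remain.

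**The case against.** The strongest reply is that the reported ADA results largely escape the problem. A reader might infer from the TEAE limit that published ADA incidence is biased downwards. The documents do not support that. SAP 2.4.7 uses all samples, its only patient-level incidence line is the treatment-emergent one, and the persistence and time-to-onset lines follow the same definition. Results by time point would show a Week 35 positive in any case. This part of the objection stands in full.

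The wording also looks like shorthand, not a decision to discard follow-up data. The bullets under the ADA-positive sentence themselves refer to follow-up samples, and on the nominal schedule the TEAE end and the Week 35 visit coincide. That is fair, but it supports correcting the phrase.

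Early stoppers are not left without low-drug samples inside the TEAE period. They have a premature end-of-treatment visit that includes ADA. With a last dose between Weeks 12 and 16, their on-schedule Week 24 sample comes 84 to 56 days later (about 2% to 7.5% of drug remaining on the 15-day half-life). This also stands.

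Nor can Week 35 be called the most informative sample on this evidence. The half-life is from single doses in healthy subjects, the assay's drug tolerance is not given, and Protocol 9.3.1.3.2 says interference will be taken into account in interpretation.

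Finally, no rate of misclassification can be borrowed. The first-in-man study found ADA in 4 of 36 subjects, but the repeat-dose study in IPF reported no significant emergent ADA reactivity, and neither says how many were first positive late.

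**Conclusion.** The inconsistency is real and minor. As written, SAP 2.1.7 would label a patient first positive more than 84 days after the last dose as ADA negative or inconclusive, while counting the same patient as treatment-emergent positive. The samples exposed are the Week 35 sample of any early stopper, the Week 24 sample as well if the last dose was at Week 11 or earlier, and the Week 35 sample of a completer seen more than 84 days after the last dose.

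The effect is limited to the ADA positive/negative patient classification and to anything described only for ADA-positive patients, such as titer and neutralizing status if those are read at patient level. The treatment-emergent incidence table and the efficacy analyses are unaffected. The 40% rests on equally likely offsets, and the 4.7 per arm rests on the plan's 10% discontinuation and full attendance. Neither converts into a number of patients or a shift in a rate.

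**What to change.** In the ADA-positive sentence of SAP 2.1.7, replace *during the TEAE period* with *in any post-first-dose sample up to and including the Week 35 follow-up sample*. Both definitions then share one time limit and agree with SAP 2.4.7 and with the references to follow-up samples already in 2.1.7.

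The cost is one phrase. No new data or analysis is needed, and the treatment-emergent count in 2.4.7 does not change. The number of patients labelled ADA positive can only stay the same or rise to match it.

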1.2 STUDY FLOW CHART

Period	Screening	Baseline visit	Treatment period									FU	
Visits/phone calls	V1	V2 ^{a,b}	V3	V4	Phone call	V5	V6 ^r	Phone call	IVRS call ^r	Phone call	V7 ^s (EOT)	Phone call	V8 (EOS)
Day/Week	D-28 to D-1	D1	W2	W4	W6	W8	W12	W16	W18	W20	W24	W30	W35
Informed consent	X												
Patient Demography	X												
Medical/surgical history	X												
Prior/concomitant medications	X	X	X	X	X	X	X	X		X	X	X	X
Inclusion/exclusion criteria	X	X											
Randomization		X											
Call IVRS	X	X	X	X		X	X		X		X		X
Study treatment administration													
SAR156597 or placebo ^c		A-----/E											
Safety													
Physical examination ^d	X	X	X	X		X	X				X		X
Vital signs ^e	X	X	X	X		X	X				X		X
ECG ^f	X	X		X		X	X				X		X
Echocardiogram ^g	X												
Hematology, biochemistry, urinalysis ^h	X	X		X		X	X				X		X
Serology tests ⁱ	X												
Tuberculosis screen ^k	X												
β -HCG blood test ^l	X												
Urine pregnancy test ^l		X		X		X	X	X		X	X		X
Review patient booklet (Local tolerability of SC)		X (post-dose)-----/E											

injections/IMP compliance) ^m			Treatment period											
Period	Screening	Baseline visit											FU	
Visits/phone calls	V1	V2 ^{a,b}	V3	V4	Phone call	V5	V6 ^r	Phone call	IVRS call ^r	Phone call	V7 ^s (EOT)	Phone call	V8 (EOS)	
Day/Week	D-28 to D-1	D1	W2	W4	W6	W8	W12	W16	W18	W20	W24	W30	W35	
Adverse event reporting	X	X	X	X	X	X	X	X	X	X	X	X	X	
Pharmacokinetics														
Blood samples for PK		X		X		X	X				X		X	
Blood samples for ADA	X	X		X		X	X				X		X	
Efficacy														
mRSS	X	X		X		X	X				X		X	
SHAQ		X		X		X	X				X		X	
PFTs (FVC & DLco)	X	X					X				X		X	
UCLA SCTC GIT 2.0		X		X		X	X				X		X	
Digital Ulcer Count		X		X		X	X				X		X	
Tender Joint Count 28		X		X		X	X				X		X	
CRISS ⁿ							X				X		X	
Patient Global Assessment ^o		X		X		X	X				X		X	
Physician Global Assessment ^p		X		X		X	X				X		X	
EQ-5D-5L		X					X				X		X	
Resource Utilization ^q		X					X				X		X	
Blood samples for protein biomarkers analysis		X					X				X		X	
Future Use of Sample: Archived blood samples for future protein assays and mRNA (Optional and requires signing of separate ICF)		X					X						X	

a Randomization/baseline Visit is defined as Day 1. Visit windows for subsequent visits are ± 2 days

b All assessments at Visit 2 (Day 1) are to be conducted pre dose with the exception of the assessment of local tolerability of SC injections

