2 STATISTICAL AND ANALYTICAL PROCEDURES

2.1 ANALYSIS ENDPOINTS

2.1.1 Demographic and baseline characteristics

The baseline value is defined as the last available value before the first administration of the Investigation Medicinal Product (IMP).

All baseline safety and efficacy parameters are presented along with the on-treatment summary statistics in the safety and efficacy sections ([Section 2.4.4](#) and [Section 2.4.5](#)).

Demographic characteristics

Demographic variables are gender (Male, Female), ethnicity (Hispanic or Latino, Not Hispanic or Latino, Not reported, Unknown), race (American Indian or Alaska Native, Asian, Black or African American, Native Hawaiian or other Pacific Islander, White, Not reported, Unknown), age in years (quantitative and qualitative variable: <45, [45-65[, [65-75[and ≥ 75 years) and Body Mass Index (BMI) in kg/m² (quantitative variable and qualitative variable: <30 and ≥ 30).

Medical or surgical history

Medical (or surgical) history includes previous relevant medical and surgery history collected at baseline.

This information will be coded using the version of Medical Dictionary for Regulatory Activities (MedDRA) currently in effect at Sanofi at the time of database lock.

Disease characteristics at baseline

Specific disease history includes disease duration from the time of first non-Raynaud's phenomenon manifestation (months), any systemic sclerosis history and mRSS at baseline. The auto-antibodies specific to systemic sclerosis (centromere antibodies, RNA polymerase III antibody, Scl-70 antibody and ANA staining pattern) and stratification factor (with/without medical history of SSc-ILD) as per IRT and as per electronic case report form (e-CRF) will be also presented.

Alcohol habits at baseline

Alcohol habits (frequency of alcoholic drinks in the last 12 months (Never/At least monthly/At least weekly/At least daily/Occasionally), number of standard drinks (1 or 2/Greater than 2 where standard drink means 1 pint/bottle of beer, 1 glass of wine, 1 shot of hard liquor...) per day when drinking alcohol.

Other baseline characteristics

Other baseline characteristics include weight in kilograms (quantitative variable and qualitative variable: <50, [50-100[, ≥100).

Any technical details related to computation, dates, and imputations for missing dates are described in [Section 2.5](#).

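### Read literally, SAP 2.1.7 dates the onset of a treatment-boosted ADA response at or before the first dose, not at the boost

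*SAP*

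**What the plan says.** SAP 2.1.7 gives two routes to a treatment-emergent ADA response. The first is no positive response at baseline followed by any positive sample. The second is "Patients with a positive ADA response at baseline and at least a specific increase" in titer afterwards, for example 4-fold under a 2-fold dilution scheme. The same section describes the boosted case as "Pre-existing ADAs that were boosted to a higher level following administration of biotherapeutic".

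It then defines, for the combined group, "Time to onset of treatment-emergent ADA positive response (in days): date of first ADA positive - date of first IMP administration". SAP 2.4.7 tabulates this variable: "Time to onset of treatment-emergent ADA positive response (in days) using descriptive statistics by treatment arm and also according to peak titer". The lead-in to that list takes all samples, whatever their timing relative to injections.

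On baseline, SAP 2.1.1 states "The baseline value is defined as the last available value before the first administration" of study drug, and Table 3 in SAP 2.5.4 uses the same rule. Protocol 1.2 adds "All assessments at Visit 2 (Day 1) are to be conducted pre dose". Protocol 9.3.1.1 schedules a further ADA sample at screening.

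The duration variable in SAP 2.1.7 is computed as "date of last treatment induced ADA sample minus date of first treatment induced or treatment boosted ADA sample + 1", under a description that refers to induced ADA only.

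**The concern.** The onset formula suits a patient who starts negative and becomes positive. It does not suit a patient who starts positive, because that patient's first positive sample is the baseline sample and says nothing about when the titer rose. The treatment-emergent definition contains both kinds of patient, and one formula is applied to both.

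A literal implementation would mix real onset times with zeros in the summary by arm and by peak titer. One boosted patient is enough to set the minimum of that summary at 0 or below. How far the median moves depends on the boosted share, which the documents do not give. Immunogenicity is a stated secondary objective, so the table will be read. If a programmer corrects the rule silently, the reported variable no longer matches the SAP, and two programmers could correct it differently.

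The duration formula has a related inconsistency: its start date admits boosted samples and its end date does not.

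**Working it through.** The plan states no figure to reproduce here. The check applies the stated rule to the scheduled sampling days.

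**Inputs**
- First dose: Day 1 (SAP 2.5.1).
- Baseline ADA sample: Day 1 before dosing, or screening (Day -28 to Day -1) if no Day 1 result is available (Protocol 1.2 and 9.3.1.1; SAP 2.1.1 and 2.5.4).
- Post-dose ADA samples: Weeks 4, 8, 12, 24 and 35 (Protocol 1.2), with target study days 29, 57, 85, 169 and 246 (SAP Table 3).
- Assumed for illustration: 2-fold dilution, so a boost is at least a 4-fold titer rise.

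**Rule as written:** onset = date of first ADA-positive sample minus date of first dose.

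**Rule dated from the response:** onset = date of first post-dose sample meeting the treatment-emergent definition minus date of first dose.

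**Example.** Titer 20 on Day 1 before dosing; titer 80 (80/20 = 4-fold) first seen on Day 85. As written: Day 1 - Day 1 = 0 days. Dated from the boost: Day 85 - Day 1 = 84 days.

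| Boost first seen | Target day | As written, Day 1 sample positive | Dated from the boost |
|---|---|---|---|
| Week 4 | 29 | 0 | 29 - 1 = 28 |
| Week 8 | 57 | 0 | 57 - 1 = 56 |
| Week 12 | 85 | 0 | 85 - 1 = 84 |
| Week 24 | 169 | 0 | 169 - 1 = 168 |
| Week 35 | 246 | 0 | 246 - 1 = 245 |

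The third column does not depend on when the boost occurs. If screening supplies the only baseline sample, it becomes a value between -28 and -1.

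**Control case.** A treatment-induced patient, negative at screening and on Day 1 and first positive at Week 8, gets 57 - 1 = 56 days under both rules. The formula works for that patient.

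**Duration.** The start date is the first induced or boosted sample; the end date is the last induced sample. A patient with boosted samples only has a start date and no end date.

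**The case against.** The best defence is context. The variable is labelled as the onset of a treatment-emergent response, and SAP 2.1.7 opens by defining ADA-positive patients through at least one induced or boosted sample. On that reading the first ADA positive means the first qualifying sample, and no pre-dose sample could count. This is probably what was intended. But the opening sentence classifies patients, not samples; the same section speaks of a positive response at baseline; and SAP 2.4.7 excludes no pre-dose sample. The duration item just before it does specify induced or boosted samples for its start date, so the precise wording was at hand and the onset item lacks it.

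Second, Protocol 11.4.4 limits the kinetics of the immune response to treatment-induced ADAs, for whom the formula normally works. That stands. It makes restricting the variable as legitimate a repair as redefining it. It does not rescue the SAP text, which extends onset to all treatment-emergent responses.

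Several stronger readings are tempting and are not supported:

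- **Negative onsets would be common.** Table 3 allows a single baseline value, the last before first dose. With a usable Day 1 sample the literal result is 0, so negative values mainly need a missing or non-reportable Day 1 sample.
- **The error is always between 28 and 245 days.** These are target-day values. The ±2-day visit window and the unscheduled ADA samples in Protocol 10.6.3.2 allow less than 28, and a screening-only baseline allows up to 245 + 28 = 273.
- **The whole placebo column would be at or below 0.** Protocol 9.3.1.3.2 says "Placebo samples will only be analyzed at baseline, and will continue to be followed if the baseline time point results positive for ADA", so on scheduled samples a placebo response could arise only through the baseline-positive route. But it would need a two-step titer rise without active drug, and the column may well be empty.
- **The lack of a duration for boosted patients is an error.** The item is described as the longevity of induced ADA, so leaving them out may be deliberate. What stands is only that its two ends name different populations.

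**Conclusion.** The point holds as a defect in a stated rule. Taken literally, SAP 2.1.7 gives any boosted patient an onset of 0 days, or a negative value if screening supplies the only baseline sample, where dating from the boost would give about 28 to 245 days on target visit days. No other text in the SAP corrects this.

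Its reach is small. The number of boosted patients is unknown and may be zero in either arm, so no shift in the median can be claimed. The effect is confined to a descriptive summary. Treatment-induced patients who are negative before dosing are dated correctly, ADA incidence and titer summaries do not use this variable, and the primary endpoint, alpha and power are untouched.

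The conclusion assumes that the formula is programmed as written and that pre-dose positive samples count as ADA positive, as the SAP's own wording for baseline indicates.

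**What to change.** In SAP 2.1.7, adopt one of two repairs for onset:

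1. Define it as the date of the first post-dose sample that meets the treatment-emergent definition, minus the date of first dose. That sample is the first positive one if baseline is negative, and the first with the required titer increase if baseline is positive.
2. Restrict the variable to treatment-induced patients, in line with Protocol 11.4.4, and relabel it here and in SAP 2.4.7.

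For duration, name the same population at both ends: induced only, or induced and boosted, consistent with the choice made for onset.

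The cost is two wording edits and the matching programming specification, with a label change in SAP 2.4.7 if the second option is taken. No new samples, assays or data are needed.
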